| Randomized Order | | |
| 2 | 0 (placebo) | 0 (placebo) |
| 3 | 0 (placebo) | 10mg |
| 4 | 4mg | 10mg |

approximately 0930 participants will complete baseline QST, physical functioning measures, and self-report measures (see below). The second 10-14mL blood draw (for those in the pK group) will be collected and then two oral capsules containing either active drug or placebo (randomized in sessions 2-4) will be administered at approximately 1100. Briefly, subjects will complete QST, physical functioning, cognitive testing, self-report, and vital sign measures (as well as blood draws for those in the pK group) at regular intervals following study drug administration. Self-report measures will include specific opioid agonist and antagonist effects, to assess whether cannabinoids

are exerting an effect on a particular category of opioid agonist symptom, and will capture whether any negative effects (e.g., nausea) occur. Frequent collection will enable evaluation of time to peak drug effects, duration of effects, and general time course of effects and is a widely used and accepted approach in laboratory studies of drug effects. During the final assessment each day, subjects will complete a Drug vs. Money Questionnaire to indicate the dollar value they would place upon the drug received⁹⁸, which is a well-accepted proxy measure of abuse liability. Study staff will document adverse events throughout the study and any subject who experiences a strongly unpleasant effect of the medications, or wishes to discontinue for any reason will be able to end participation at any time. Any subject who is experiencing strong agonist effects at the end of the session will be provided overnight accommodation in the Clinical Research Unit (CRU; which is located on our campus and with whom we have frequent collaborations); based on our experience we expect this to be rare and are budgeting for 20% of sessions to undergo a one-night CRU stay.

Measures

Pilot testing indicates it takes approximately one hour to complete the assessment battery (see Table 2).

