This will be the first study to examine interactions between cannabinoids and opioids on clinical and laboratory-evoked measures of pain in a population who has chronic pain and central sensitization. The study uses a within-subject, placebo-controlled design and no data exist upon which to generate a power analysis. We have selected two primary outcomes for the measurement of analgesia: measures of conditioned pain modulation and time to hand withdraw latency in a cold presser test.

[name], a biostatistician with extensive experience analyzing within-subject laboratory tests of drug effects, conducted a revised power calculation based on new literature that employs methods similar to those of this study (Cooper et al., 2018). Sample size estimates were premised with a power of 0.8, alpha =0.05 and calculated effect sizes (Cohen, 1988). These analyses suggests a sample size ranging from 10-15 individuals would be sufficient to detect large effect sizes. Because one of our aims focuses on a sex-comparison, we originally planned to double our enrollment. Thus, our sample of 64 completers (32/sex) will yield sufficient power to evaluate direct effects of study condition on CPM and cold presser in both Phases, even at small effect size levels, and will also be sufficient to identify between-session differences on pK results¹⁴⁰.

d. Early stopping rules.

The safety of participants is the highest priority. The largest potential risk of this study is cardiovascular in nature. This notion is based upon the results of a published study that reported an increase in heart rate and blood pressure among patients exposed to the cannabinoid dronabinol who were also undergoing opioid withdrawal (of which increased heart rate and blood pressure is a known symptom). This group differs from our target population in many ways, however out of an abundance of caution in these early studies, we will use this experience to inform our safety criteria. We will monitor vital signs at all study data collection time points and will follow procedures that we have developed and successfully used in previous studies that administered drugs (e.g., cocaine) with known cardiovascular risks. Specifically, if a participant's parameters reach these thresholds, then a study physician, who will always be available via telephone, will be contacted and consulted to determine the appropriate course of action.

- Systolic blood pressure: $\geq 180\text{mm Hg}$

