a. Hydromorphone: Administration of any drug involves some risk because it is not always possible to predict individual response to drugs. The most likely risk in this study is that subjects will experience side-effects of the drugs that may be unpleasant. Common side effects of hydromorphone are light-headedness, dizziness, sedation, nausea, vomiting, sweating, flushing, dysphoria, euphoria, dry mouth, and pruritus. Less frequently observed side effects are weakness, headache, agitation, tremor, uncoordinated muscle movements, alterations of mood (nervousness, apprehension, depression, floating feelings, dreams), muscle rigidity, paresthesia, muscle tremor, blurred vision, nystagmus, diplopia and miosis, transient hallucinations and disorientation, visual disturbances, insomnia, increased intracranial pressure, flushing of the face, chills, tachycardia, bradycardia, palpitation, faintness, syncope, hypotension, hypertension, bronchospasm and laryngospasm, constipation, biliary tract spasm, ileus, anorexia, diarrhea, cramps, taste alteration, urinary retention or hesitancy, antidiuretic effects, urticaria, other skin rashes and diaphoresis. Side effects of hydromorphone are generally temporary, dissipate within several hours, and are dose-dependent. Thus, participants may only experience side-effects occasionally during the research study. Serious potential adverse effects of hydromorphone administration that are possible but extremely unlikely to be encountered in this study are respiratory depression and loss of consciousness. The FDA has identified the following conditions as increasing the risk for respiratory depression or other serious side effects following hydromorphone administration: patients with status asthmaticus; chronic obstructive pulmonary disease; reduced respiratory function; high blood pressure; impairment of hepatic, pulmonary or renal functions; myxedema or hyperthyroidism; adrenocortical insufficiency; gall bladder disease; acute alcoholism; history of convulsive disorders; history of head injury; currently taking sedatives, hypnotics or phenothiazines; and sulfite allergy. Mean exposure to hydromorphone is also increased 4-fold among patients with hepatic impairment and 3-fold among patients with renal impairment. The BPRU has extensive experience administering hydromorphone to opioid naïve individuals and employs well-established and rigorous eligibility criteria to ensure that individuals who may be more prone to experiencing opioid-induced side effects will not be admitted into the study.

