
The most serious potential adverse event following hydromorphone administration is opioid agonist overdose, which is characterized by respiratory depression, somnolence progressing to stupor or coma, skeletal muscle flaccidity, cold and clammy skin, constricted pupils, and sometimes bradycardia and hypotension. In serious overdosage, particularly following intravenous injection, apnea, circulatory collapse, cardiac arrest, and death may occur. We believe the risk of overdose in this study to be low for the following reasons: we have extensive experience in the administration of hydromorphone, we have chosen a dose that has been demonstrated to be safe and tolerable in similarly opioid inexperienced participant populations, we will exclude any individual who has a medical condition that may increase the risk for respiratory depression and/or other adverse events, all medication doses will be administered by a trained research nurse, and participants will be closely monitored by trained staff who will have access to

the opioid antagonist naloxone to reverse the opioid agonist effects. Additional protections against the risk of hydromorphone side effects, including overdose, are discussed in the Protection Against Risks section. Hydromorphone has no known interactions with dronabinol.

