b. Dronabinol: The FDA identifies the following adverse effects of dronabinol: cardiovascular (hypertension, hypotension, palpitations, tacharrhythmia, vasodilation); dermatologic (flushing); gastrointestinal (abdominal pain, nausea, vomiting, xerostomia); neurological (amnesia, ataxia, confusion, coordination problem, dizziness, somnolence, vertigo), and psychiatric (anxiety, delusion of persecution, depersonalization, depression, disturbance in thinking, euphoria, hallucinations), though it should be noted that the adverse effects were collected from studies of patients undergoing chemo therapy or with advanced HIV, which may have decreased their threshold for experiencing negative effects. Dronabinol is listed as pregnancy category C, meaning that preclinical studies have revealed adverse effects on the fetus but that no controlled human studies have been conducted to assess this risk (pregnancy or breast-feeding will be an exclusion criterion). The only absolute contraindication of dronabinol is allergy or hypersensitivity to cannabinoids or sesame oil. Dronabinol has moderate – severe interactions with breast cancer resistance protein inhibitors (topotecan, ataluren), and has moderate interactions with the antiretroviral protease inhibitor ritonavir (Norvar), which is used to treat HIV and AIDS.

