c. Opioid-Cannabinoid Interactions: There are limited data available to indicate whether there are consistent opioid-cannabinoid interactions on physiological outcomes. One study that was published in 1975 evaluated combinations of delta-9 THC (which is present in smoked marijuana and dronabinol) and the opioid oxymorphone reported that the combination of drugs decreased CO₂ slope and increased tachycardia, though heart rate increased generally following exposure to delta-9 THC¹⁴¹. A second, more recently published study reported that a 40mg dose dronabinol that was administered to participants undergoing opioid withdrawal (as a method of minimizing the withdrawal syndrome) also produced tachycardia¹⁴². This effect was eliminated once the dose of dronabinol was reduced to 30mg. We do not believe this will be a problem for this study. The second study only reported negative effects when dronabinol was administered at the highest dose approved for human consumption by the FDA (40mg) and the effect was completely eliminated once the dose was marginally reduced. In addition, this study enrolled patients who were opioid dependent and withdrawing from opioids, and increases in heart rate and blood pressure are well-recognized symptoms of the opioid withdrawal syndrome. Thus, though we have presented these studies to be transparent, we do not believe their results will necessarily generalize to our patient population. We have listed our protections against risk in the following section.

d. Chance That Participants May Begin Abusing Opioids or Cannabinoids Following Exposure to Study Drugs: There is a small but potential risk that exposing non-drug abusing individuals to doses of hydromorphone or cannabinoids may elicit reinforcing effects that could precipitate subsequent drug-use behavior. Enrolling non-drug users into controlled laboratory studies is a conventional strategy that has been used extensively to evaluate the abuse liability potential of numerous drugs of abuse both within our laboratory and by other laboratories.

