extensive experience administering this dose at controlled levels in healthy controls. Second, we have developed several standard criteria that are followed by nursing staff and research personnel to monitor participants who have been provided with a study medication. All nursing and research staff are informed of these standards, and a list of these standards is posted in each testing room. The standards are as follows: If respiratory rate drops below 12 breaths/minute and is accompanied by sedation, participants are prompted verbally to breath. In our experience, verbal and physical stimulation is often sufficient to prompt breathing and restore a normal respiratory rate. If respiratory rate drops further and/or if oxygen saturation rates fall below 90% saturation, then patients are monitored carefully. Specifically, they will be accompanied continuously by a medical and/or nursing staff member, evaluated by a staff physician, and are given supplemental oxygen at 2L/min via a nasal cannula (available on site in the exam testing room) if deemed necessary by the physician. If clinical evaluation determines that a participant's sedation level is increasing, the opioid antagonist naloxone can be promptly administered via intramuscular route to produce an immediate reversal of opioid effects. There have been very few incidents throughout our >15 year experience administering opioid agonists to human participants in controlled laboratory conditions that have necessitated actual intervention (oxygen and/or naloxone), however our equipment and medical/nursing staff is always prepared for this possibility. We feel these procedures will sufficiently protect participants from possible adverse and serious adverse events.

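### The blood pressure and heart rate triggers for calling the physician are all upper limits; no lower limit is set, although hypotension is listed for both drugs and bradycardia for hydromorphone

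*Combined protocol and SAP*

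**What the plan says.** Section 7.d (Early stopping rules) names cardiovascular effects as the largest potential risk. It bases its criteria on a published report of raised heart rate and blood pressure in patients given dronabinol during opioid withdrawal. It commits to regular measurement: "We will monitor vital signs at all study data collection time points". If a participant's "parameters reach these thresholds, then a study physician, who will always be available via telephone, will be contacted and consulted". Three thresholds follow:

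- systolic pressure of 180 mm Hg or more;
- diastolic pressure of 120 mm Hg or more;
- heart rate at or above 220 − (age × 0.85).

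Section 8.a lists possible drug effects. The less frequent effects of hydromorphone include "tachycardia, bradycardia, palpitation, faintness, syncope, hypotension, hypertension". Its overdose picture includes "constricted pupils, and sometimes bradycardia and hypotension". The dronabinol list has "cardiovascular (hypertension, hypotension, palpitations, tacharrhythmia, vasodilation" among others.

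Section 8.b (Protection Against Hydromorphone Risks) sets out the standards posted in each testing room. The first reads: "If respiratory rate drops below 12 breaths/minute and is accompanied by sedation, participants are prompted verbally to breath". A further fall in respiratory rate, or saturation below 90%, leads to continuous staff presence and evaluation by a physician. If sedation is judged to be increasing, naloxone can be given. Blood pressure and pulse do not appear in these standards.

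Section 8.b (Protection Against Dronabinol Risks) adds a vital signs monitor and readings every 15 minutes for the first 2 hours, without numeric limits. It also plans a review after 5 participants, which looks for tachycardia only.

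**The concern.** Both drugs can lower blood pressure according to the protocol's own risk section, and hydromorphone can also slow the pulse. The rule that tells staff when they must call a physician covers only movement in the other direction. The breathing, saturation and sedation standards would probably catch an opioid overdose in which low pressure is one sign among several. They would not catch a low pressure or pulse on its own.

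Participants are 45 or older and have knee osteoarthritis (section 5). The Timed Up and Go (TUG), stair climb and 3-minute walk are done at baseline and again at projected peak effect (section 4.a, Physical Performance Measures). Followed to the letter, the plan lets someone with a markedly low reading start these tests with no physician consulted. What is at stake is participant safety during the session; no estimate or test depends on it.

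**Working it through.** This is a check of written rules; the plan gives no figure to reproduce.

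**Step 1. Direction of every rule on vital signs or sedation.**

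| Rule | Where | Direction |
|---|---|---|
| Systolic ≥ 180 mm Hg | 7.d | upper |
| Diastolic ≥ 120 mm Hg | 7.d | upper |
| Heart rate ≥ 220 − (age × 0.85) | 7.d | upper |
| Respiratory rate < 12/min with sedation | 8.b, hydromorphone | lower |
| Oxygen saturation < 90% | 8.b, hydromorphone | lower |
| Increasing sedation | 8.b, hydromorphone | clinical, no number |
| Tachycardia review after 5 participants | 8.b, dronabinol | upper, no number |

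Upper limits among the 7.d triggers: 3 of 3. Lower limits for blood pressure or heart rate anywhere in the document: 0.

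**Step 2. The heart rate ceiling as printed.**

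- Age 45: 220 − 45 × 0.85 = 220 − 38.25 = 181.75
- Age 60: 220 − 60 × 0.85 = 220 − 51 = 169
- Age 75: 220 − 75 × 0.85 = 220 − 63.75 = 156.25

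It is an upper bound at each age.

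**Step 3. Illustrative readings against the rules.** The readings are assumed and are not proposed limits. Each is paired with respiratory rate 14/min, saturation 97%, an alert participant and sedation not increasing.

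| Systolic / diastolic / pulse | 7.d triggers met (ages 45, 60, 75) | Posted criteria met |
|---|---|---|
| 100 / 60 / 55 | 0 of 3 | 0 of 3 |
| 90 / 55 / 50 | 0 of 3 | 0 of 3 |
| 80 / 45 / 42 | 0 of 3 | 0 of 3 |
| 70 / 40 / 35 | 0 of 3 | 0 of 3 |

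The zeros follow by construction, since a low value cannot meet an upper limit. The table shows only that however low the pressure and pulse go, the written rules stay silent while breathing, saturation and alertness are normal.

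**Step 4. Would the low reading be seen?** Yes. Section 4.a plans "vital sign measures (as well as blood draws for those in the pK group) at regular intervals following study drug administration", and section 8.b adds the 15-minute readings in the first 2 hours. The data exist; what is missing is the value at which staff must act. Dronabinol is stated to peak at 2 to 4 hours (section 6), so its peak falls largely after the 15-minute schedule has ended.

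**The case against.** The strongest reply is that the upper limits are a reasoned choice. Section 7.d names its source, and both opioid-cannabinoid studies described in section 8.a report tachycardia. The most serious opioid hazard, overdose, is covered by the breathing, saturation and sedation standards, with oxygen and naloxone at hand. Hypotension and bradycardia appear only among many less frequent hydromorphone effects or as part of overdose, and a numeric limit for every listed effect would be excessive.

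Nor does the plan restrict calls to the listed thresholds. A physician is always reachable by telephone, adverse events are documented throughout, and participants can be withdrawn or discharged if their risk changes (sections 4.a, 4.f and 7.d). There are many protections:

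- Before dosing, a history, physical, ECG and blood tests are done.
- Significant arrhythmia, vasospastic disease, an abnormal ECG or other risk-raising illness excludes a person, as do earlier negative effects of cannabinoid products.
- A trained research nurse gives every dose, with close monitoring.
- Hydromorphone is given first with placebo.
- No moderate or serious effects have been seen in a current study using an identical hydromorphone dose.
- The stairs have hand rails, and participants may stop any task.

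Much of this stands. It explains why upper limits are there, and it makes the gap small. It does not explain why lower limits are absent. Entry screens act before the session. The hydromorphone-first session and the reassuring experience concern hydromorphone, while dronabinol and the combination come in sessions 2 to 4. The discretionary routes leave blinded staff to decide how low is too low. The team already uses numeric lower limits for breathing and saturation, so lower limits for pressure and pulse would follow its own practice.

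**Conclusion.** The concern holds. All 3 blood pressure and heart rate triggers are upper limits, the document has no lower limit for either, and section 8.a lists hypotension for both drugs and bradycardia for hydromorphone. The gap is confined to an isolated low pressure or pulse in an alert participant with normal breathing and saturation.

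These are counts of rules, not an estimate of risk. The documents give no frequency of isolated hypotension or bradycardia at these doses, so none is offered. Sample size and planned analyses are unaffected. The change should be made because it is cheap and improves safety; the trial's conclusions do not depend on it. The textual absence is certain; its practical importance is modest.

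**What to change.** Make the list in section 7.d and the posted standards in section 8.b two-sided. Add lower limits for systolic pressure, diastolic pressure and heart rate at which the study physician must be called. The study medical team should set the values; none are proposed here because the documents give no basis for them. Apply the limits to all vital signs already scheduled, including those at the peak-effect assessment before the physical tests.

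The cost is a protocol amendment and an update of the posted list. The readings and the on-call physician are already in place. Expect a few more calls and an occasional delayed or missed physical test at peak. TUG time from pre-dose to peak is the primary outcome for Hyp3 (section 7.a), and losses caused by low readings may depend on drug condition. Record the reason for each delayed or missed peak TUG, so that such losses can be seen and taken into account.

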a. Hydromorphone: Administration of any drug involves some risk because it is not always possible to predict individual response to drugs. The most likely risk in this study is that subjects will experience side-effects of the drugs that may be unpleasant. Common side effects of hydromorphone are light-headedness, dizziness, sedation, nausea, vomiting, sweating, flushing, dysphoria, euphoria, dry mouth, and pruritus. Less frequently observed side effects are weakness, headache, agitation, tremor, uncoordinated muscle movements, alterations of mood (nervousness, apprehension, depression, floating feelings, dreams), muscle rigidity, paresthesia, muscle tremor, blurred vision, nystagmus, diplopia and miosis, transient hallucinations and disorientation, visual disturbances, insomnia, increased intracranial pressure, flushing of the face, chills, tachycardia, bradycardia, palpitation, faintness, syncope, hypotension, hypertension, bronchospasm and laryngospasm, constipation, biliary tract spasm, ileus, anorexia, diarrhea, cramps, taste alteration, urinary retention or hesitancy, antidiuretic effects, urticaria, other skin rashes and diaphoresis. Side effects of hydromorphone are generally temporary, dissipate within several hours, and are dose-dependent. Thus, participants may only experience side-effects occasionally during the research study. Serious potential adverse effects of hydromorphone administration that are possible but extremely unlikely to be encountered in this study are respiratory depression and loss of consciousness. The FDA has identified the following conditions as increasing the risk for respiratory depression or other serious side effects following hydromorphone administration: patients with status asthmaticus; chronic obstructive pulmonary disease; reduced respiratory function; high blood pressure; impairment of hepatic, pulmonary or renal functions; myxedema or hyperthyroidism; adrenocortical insufficiency; gall bladder disease; acute alcoholism; history of convulsive disorders; history of head injury; currently taking sedatives, hypnotics or phenothiazines; and sulfite allergy. Mean exposure to hydromorphone is also increased 4-fold among patients with hepatic impairment and 3-fold among patients with renal impairment. The BPRU has extensive experience administering hydromorphone to opioid naïve individuals and employs well-established and rigorous eligibility criteria to ensure that individuals who may be more prone to experiencing opioid-induced side effects will not be admitted into the study.

The most serious potential adverse event following hydromorphone administration is opioid agonist overdose, which is characterized by respiratory depression, somnolence progressing to stupor or coma, skeletal muscle flaccidity, cold and clammy skin, constricted pupils, and sometimes bradycardia and hypotension. In serious overdosage, particularly following intravenous injection, apnea, circulatory collapse, cardiac arrest, and death may occur. We believe the risk of overdose in this study to be low for the following reasons: we have extensive experience in the administration of hydromorphone, we have chosen a dose that has been demonstrated to be safe and tolerable in similarly opioid inexperienced participant populations, we will exclude any individual who has a medical condition that may increase the risk for respiratory depression and/or other adverse events, all medication doses will be administered by a trained research nurse, and participants will be closely monitored by trained staff who will have access to

the opioid antagonist naloxone to reverse the opioid agonist effects. Additional protections against the risk of hydromorphone side effects, including overdose, are discussed in the Protection Against Risks section. Hydromorphone has no known interactions with dronabinol.

b. Dronabinol: The FDA identifies the following adverse effects of dronabinol: cardiovascular (hypertension, hypotension, palpitations, tacharrhythmia, vasodilation); dermatologic (flushing); gastrointestinal (abdominal pain, nausea, vomiting, xerostomia); neurological (amnesia, ataxia, confusion, coordination problem, dizziness, somnolence, vertigo), and psychiatric (anxiety, delusion of persecution, depersonalization, depression, disturbance in thinking, euphoria, hallucinations), though it should be noted that the adverse effects were collected from studies of patients undergoing chemo therapy or with advanced HIV, which may have decreased their threshold for experiencing negative effects. Dronabinol is listed as pregnancy category C, meaning that preclinical studies have revealed adverse effects on the fetus but that no controlled human studies have been conducted to assess this risk (pregnancy or breast-feeding will be an exclusion criterion). The only absolute contraindication of dronabinol is allergy or hypersensitivity to cannabinoids or sesame oil. Dronabinol has moderate – severe interactions with breast cancer resistance protein inhibitors (topotecan, ataluren), and has moderate interactions with the antiretroviral protease inhibitor ritonavir (Norvar), which is used to treat HIV and AIDS.

c. Opioid-Cannabinoid Interactions: There are limited data available to indicate whether there are consistent opioid-cannabinoid interactions on physiological outcomes. One study that was published in 1975 evaluated combinations of delta-9 THC (which is present in smoked marijuana and dronabinol) and the opioid oxymorphone reported that the combination of drugs decreased CO₂ slope and increased tachycardia, though heart rate increased generally following exposure to delta-9 THC¹⁴¹. A second, more recently published study reported that a 40mg dose dronabinol that was administered to participants undergoing opioid withdrawal (as a method of minimizing the withdrawal syndrome) also produced tachycardia¹⁴². This effect was eliminated once the dose of dronabinol was reduced to 30mg. We do not believe this will be a problem for this study. The second study only reported negative effects when dronabinol was administered at the highest dose approved for human consumption by the FDA (40mg) and the effect was completely eliminated once the dose was marginally reduced. In addition, this study enrolled patients who were opioid dependent and withdrawing from opioids, and increases in heart rate and blood pressure are well-recognized symptoms of the opioid withdrawal syndrome. Thus, though we have presented these studies to be transparent, we do not believe their results will necessarily generalize to our patient population. We have listed our protections against risk in the following section.

d. Chance That Participants May Begin Abusing Opioids or Cannabinoids Following Exposure to Study Drugs: There is a small but potential risk that exposing non-drug abusing individuals to doses of hydromorphone or cannabinoids may elicit reinforcing effects that could precipitate subsequent drug-use behavior. Enrolling non-drug users into controlled laboratory studies is a conventional strategy that has been used extensively to evaluate the abuse liability potential of numerous drugs of abuse both within our laboratory and by other laboratories.

e. Discomfort from Pain Testing: Participants will likely find the pain testing procedures uncomfortable for a brief period of time. This effect is expected to be transient and to produce only mild levels of discomfort. Pressure Pain Testing: There is a slight chance of mild transient bruising associated with use of the algometer. In our experience, this is quite rare (< 5 % of cases). Thermal Pain testing: There is a very small chance that the heating device might produce a burn, but the risks associated with the relatively small amount of heat applied to the skin (maximum of 122 degrees Fahrenheit or 51 degrees Celsius) are very low. The Medoc device has safety features built into both the hardware and software. The risks associated with use of this equipment are less than those associated with common household appliances. Punctuate Probe Pain Testing: There is a very slight chance that the probe might superficially puncture the skin for individuals with “thin skin.” Capsaicin is the main ingredient in hot peppers, and is used as an over the counter drug for the treatment of pain. The dose of capsaicin we are using is higher than what is available

over the counter, although it is less than half of the dose in a single habanera pepper. Capsaicin does cause pain, like a hot pepper may do when it is eaten. Capsaicin may produce some local redness and swelling that will disappear within a day. The area of skin where the capsaicin is applied could be sensitive for up to 48 hours. Capsaicin may cause a burning feeling in the eyes or other areas of the body if accidentally rubbed onto other skin areas. Cold Water Testing: There are no significant risks from immersion of a hand in cold water. Participants are informed that they can stop testing whenever they would like to do so. We have used the proposed laboratory pain procedures in a number of previous studies with healthy adults and chronic pain patients, including patients with KOA. No serious adverse effects were ever reported.

f. Blood draws: For participants that volunteer to undergo this part of the project, some discomfort may be associated with the drawing of blood samples, and there is a very small chance that phlebotomy may cause hematoma, infection, anemia and minor pain at the puncture site. However, these procedures are routinely performed without incident in medical settings.

g. Knee X-Rays: Knee X-rays expose participants to very low amounts of radiation. Knee x-rays will be conducted for research purposes in the current study, even though it is a procedure that would potentially be part of routine clinical care. The benefits of knee x-rays usually outweigh the minimal risk. Of note, our study physician will review incidental findings following the initial read by [name] and we will follow-up with participants/their providers as appropriate.

h. Physical Functioning Tasks: Minimal risks are associated with the 3 minute walking task, stair climb and timed up and go task. Participants may become fatigued or experience mild discomfort when completing the tasks.

i. Hair Testing: A small amount of hair will be cut from the head (not pulled). This is of minimal risk to participants.

j. Breach of Confidentiality: Although staff members are highly trained to maintain participant confidentiality, there is always a risk that some of the confidential information collected could be revealed to people who are not involved in the research study. This could be embarrassing to the participant if the participant preferred to keep his or her study participation secret, or if sensitive information became known to an individual outside the study. We have an extensive history of conducting research among substance abusers and have instituted several practices to prevent a breach from confidentiality from occurring (see below); thus, we believe this risk to be minimal.

b. Steps taken to minimize the risks.

a. Protection Against Hydromorphone Risks: We have extensive experience in the administration of hydromorphone and other opioid agonists in controlled laboratory settings and therefore anticipate few problems. Any individual who may be prone to the risks associated with hydromorphone will be excluded from participating. Although research staff and participants will be blinded to the exact medication provided, both groups will be informed of the potential side effects and risks associated with the study drug administration. Participants will be free to discontinue study participation at any time without consequence. The dose of hydromorphone that is being administered is consistent with clinical care, and is a medium level dose for the treatment of pain. Hydromorphone will always be administered along with placebo in the first session, which will provide a valuable opportunity to exclude from further participation any participant who experiences untoward effects (e.g., nausea, vomiting) resulting from that dose of hydromorphone. Great care has been taken in selecting the appropriate drug doses to ensure hydromorphone is well-tolerated and safe for our participants and participants will also be able to discontinue study participation at any time. The most serious risk associated with hydromorphone administration is respiratory depression. We believe this risk is minimal in this study for several reasons. First, we are administering a mid-level dose and have

extensive experience administering this dose at controlled levels in healthy controls. Second, we have developed several standard criteria that are followed by nursing staff and research personnel to monitor participants who have been provided with a study medication. All nursing and research staff are informed of these standards, and a list of these standards is posted in each testing room. The standards are as follows: If respiratory rate drops below 12 breaths/minute and is accompanied by sedation, participants are prompted verbally to breath. In our experience, verbal and physical stimulation is often sufficient to prompt breathing and restore a normal respiratory rate. If respiratory rate drops further and/or if oxygen saturation rates fall below 90% saturation, then patients are monitored carefully. Specifically, they will be accompanied continuously by a medical and/or nursing staff member, evaluated by a staff physician, and are given supplemental oxygen at 2L/min via a nasal cannula (available on site in the exam testing room) if deemed necessary by the physician. If clinical evaluation determines that a participant's sedation level is increasing, the opioid antagonist naloxone can be promptly administered via intramuscular route to produce an immediate reversal of opioid effects. There have been very few incidents throughout our >15 year experience administering opioid agonists to human participants in controlled laboratory conditions that have necessitated actual intervention (oxygen and/or naloxone), however our equipment and medical/nursing staff is always prepared for this possibility. We feel these procedures will sufficiently protect participants from possible adverse and serious adverse events.

b. Protection Against Dronabinol Risks: The majority of risks that are known to occur following dronabinol administration are psychiatric in nature. These risks are recognized as being transient and readily reversible. To mitigate these risks, we will exclude participants who endorse having previously experienced negative effects to cannabinoid products. We will also conduct psychiatric screening during the Screening session to ensure that patients with current or history of psychiatric events are excluded from study participation. Further, all participants will be informed about the potential side effects of the study medications and will be permitted to end study participation at any time if they experience negative events, with no consequences. Finally, we are providing participants with taxi service to and from the study sessions to ensure no persistent drug effects will impact their driving. We are also budgeting for the potential for a participant to stay the night at the CRU following study drug exposure. Based on our previous experience, we expect this to be a rare occurrence but are prepared to make that option available as needed.

To protect against risks of increased heart rate and tachycardia following co-administration of opioids and cannabinoids we will require all participants to be in good cardiovascular health prior to study enrollment (evidenced by a clean ECG, reviewed by a study physician). During sessions, all participants will be attached to a vital signs monitor and will have vital signs collected at 15 minute intervals for the first 2 hours to ensure safety. The risk of an opioid/cannabinoid interaction will only occur during a single study session, however since staff and participants will be blind as to the timing of that session, we will employ this monitoring schedule for all sessions. We will review data following completion of 5 participants and if it becomes evident that tachycardia is occurring regularly during any sessions, we will reevaluate the dose of study drugs being administered. However we believe that any changes to our dosing strategy are highly unlikely and this monitoring schedule will ensure participant safety during study participation.

c. Protection Against Risks That Participants May Begin Abusing Opioids or Cannabinoids

